#### **7.1.5 Follow-up of Events Occurring After Subject Termination of the Study**

All Adverse Events with a causal relationship to the study products or treatment procedure that the investigator becomes aware of, serious as well as non-serious, with onset after the study termination (subject's last study visit) shall be reported to the sponsor by email to [[contact]](mailto:[contact]). The investigator shall follow the subject until the event is resolved.

### 7.1.6 Pregnancy

Pregnancy itself is not regarded as an AE.

If there is a pregnancy during the study period the subject must be withdrawn from any following study treatment but should continue to be followed within the study and the outcome of pregnancy must be reported even if the delivery occurs after study completion.

A pregnancy confirmed during the study period must be reported by the investigator on a pregnancy report form immediately upon acknowledgement and be submitted to the CRO according to contact details specified below. The report can be prospective or retrospective. Follow-up shall be conducted to obtain outcome information on all prospective reports.

[figure not shown]
E-mail for pregnancy reporting:

CCI

Cases that led to fetal distress, fetal death or a congenital abnormality or birth defect are to be regarded as SAEs and shall be reported on the exposure *in utero* report form to the sponsor immediately but no later than 24 hours after the investigator's awareness. These events shall be handled as SAEs during data processing. Other complications during the pregnancy that are related to the pregnant woman and fulfills any serious criteria, such as pre-eclampsia requiring hospitalization, shall be reported and handled as SAEs. Elective abortions without complications shall not be reported as AEs.

CCI

CCI

## 7.4 Device Deficiencies

### 7.4.1 Device Deficiency Definition

A device deficiency is defined as an inadequacy of a medical device with respect to its identity, quality, durability, reliability, safetya or performance.

*Note: Device deficiencies include malfunctions, use errors or inadequate information supplied by the manufacturer.*

---

a Inadequacy of device safety refers to properties of the device which could have or have led to an AE

When a device deficiency is discovered, Part A of the clinical study complaint form shall be completed by the investigator. The type of complaint shall be described and injury to the subject or user or unintended exposure to study product shall be reported as applicable. If an injury has occurred, an AE or an SAE form shall be completed as applicable (refer to Sections 7.1.1.1 and 7.1.2.1). If no SAE was experienced as a result of the device deficiency the investigator shall assess whether or not the device deficiency could have led to an SAE if:

- Suitable action had not been taken,
- Intervention had not been made, or
- Circumstances had been less fortunate

In Part B of the clinical study complaint form, the sponsor will make the same assessment.

#### 7.4.2 Reporting of Device Deficiencies

The investigator shall send the completed clinical study complaint form to the sponsor.

E-mail for device deficiencies reporting:

CCI

A device deficiency that led to a SAE and any device deficiency that could have led to a SAE shall be reported to the sponsor within 24 hours after the investigator's awareness (for contact information, see Section 7.1.2.1).

If the investigator or the sponsor assesses that the device deficiency could have led to a SAE, the sponsor is responsible for reporting the device deficiency according to national regulations, and the PI is responsible for reporting it to the IRB/IEC.

The deficient study product shall be kept by the study site until the sponsor has confirmed whether the product shall be returned to sponsor for further study or if it can be destroyed at the study site.

#### 7.5 Urine Pregnancy Test (UPT)

For all women of childbearing potential, including those currently using contraception, a UPT is required prior to receiving study treatment at baseline and optional touch-up at Week 4. **The test result must be negative for the subject to receive any treatment with study product.** The test result will be documented in the subject's file and eCRF.

## 8. OTHER ASSESSMENTS

### 8.1 Photography

Photographs will be taken prior to the first injection of the study product, before treatments, and at every physical follow-up visit in order to document treatment effect. Photographs may also be taken to document AEs at the investigator's discretion. Baseline photographs may be used as a reference in the GAIS assessment by the investigator and subject. Site personnel will be thoroughly trained in the photographic equipment and techniques before study start.

Camera equipment will be provided by the sponsor or their designee and standardized photographs shall be achieved. Further details regarding photography procedure will be specified in a separate user guide.

## 9. STATISTICAL DESIGN AND ANALYSIS

### 9.1 General

A Statistical Analysis Plan (SAP) will be developed as a separate document. The SAP will contain a detailed and technical description regarding specific data conventions, calculations and the statistical procedures that will be used to perform the analyses that are specified in the sections below. Any changes made to the finalized SAP will be documented in the Clinical Study Report (CSR).

All statistical analyses, including summary tables and data listings, will be performed using the SAS® system. In general effectiveness, safety and baseline characteristics variables will be presented using descriptive statistics and graphs as appropriate. Continuous endpoints will be summarized using descriptive statistics, e.g. mean, median, standard deviation, minimum and maximum values. Categorical endpoints will be presented in frequency tables with number and percentage of observations for each level. 95% confidence intervals will be included when appropriate.

### 9.2 Analysis populations

The following populations will be defined:

- Modified Intention-to-treat (MITT)      Includes all subjects treated in both lips
- Safety    Includes all subjects treated in at least one lip

MITT population will be used for all effectiveness analyses. Safety analysis will be performed based on the safety population set.

The disposition of subjects will be presented in tables and/or figures as appropriate. The number of screened, treated, completed, and withdrawn subjects will be presented, as well as number of subjects in each analysis population set.

### 9.3 Demographics, baseline assessments, and subject characteristics

Demographic endpoints, baseline assessments, and subject characteristics will be presented based on the MITT population using descriptive statistics, as appropriate.

### 9.4 Data Transformations

Responder rate (%) regarding MLFS will be calculated as (number of subjects (or upper/lower lips) with at least one grade improvement from baseline/number of subjects reporting at the specified visit) \*100.

Responder rate (%) regarding WAS will be calculated as (number of subjects (or upper/lower lips) with at least one grade improvement from baseline/number of subjects reporting at the specified visit)\*100.

Responder rate (%) regarding GAIS will be calculated as (number of subjects being at least improved/number of subjects reporting at the specified visit) \*100.

The outcome of the questionnaires regarding FACE-Q will be summarized and transformed to a Rasch score (0-100).

Time to onset of an AE will be derived as the start date minus the date of most recent treatment. If the start date is missing, it will be assumed that the AE started on the day of most recent treatment.

Duration of an AE will be derived as the stop date minus the start date + 1. If the start date is missing, it will be assumed that the AE started on the day of most recent treatment. Missing stop date will not be imputed and therefore no duration will be calculated in these cases. Instead, the number of AEs that were ongoing at the end of the study will be given.

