	
Subjects will have in-clinic follow up visits at 2, 4, 8, 16, 24, 32, 40, and 48 weeks after the last injection. If a touch-up is deemed necessary and performed at 4 weeks post-baseline, a second 2-week and 4-week follow-up visits should be scheduled. See flowchart (Figure 1).
 
Safety Objective and Endpoints:
 
To evaluate the safety of Restylane Kysse for lip augmentation in Chinese subjects via assessment of:
 

• Adverse event (AE) at all study visits.

 
Safety endpoints include:
 

• Incidence, intensity, duration, and onset of related AEs collected during the entirety of the study.

 
Effectiveness Objective and Endpoints:
 

1. To evaluate the effectiveness of Restylane Kysse for lip augmentation as assessed by the investigator using the MLFS for the upper and lower lips.

	

GALDERMA EST. 1981	
Title 05DF2007 Kysse Clinical Study Protocol
 
CC1

	
Endpoints:
 
 
a. Change from baseline at 8, 16, 24, 32, 40, and 48 weeks after last injection.
 
b. Response rates (defined as at least 1-point improvement from baseline) at 8, 16, 24, 32, 40, and 48 weeks after last injection.
 
 
2. For subjects in the US: To evaluate the aesthetic improvement of the upper perioral rhytids and oral commissures after treatment with Restylane Kysse as assessed by the investigator using the WAS. Note: After baseline, WAS will only be assessed for subjects who have been treated in the upper perioral rhytids or the oral commissures.
 
Endpoints:
 
 
a. Change from baseline at 8, 16, 24, 32, 40, and 48 weeks after last injection.
 
b. Response rates (defined as at least 1-point improvement from baseline) at 8, 16, 24, 32, 40, and 48 weeks after last injection.
 
 
3. To evaluate the aesthetic improvement (overall appearance) of the upper and lower lips after treatment with Restylane Kysse as assessed by the subject and the investigator, independently, using the Global Aesthetic Improvement Scale (GAIS).
 
Endpoint:
 
 
a. Response rates (defined as at least "Improved") at 8, 16, 24, 32, 40, and 48 weeks after last injection.
 
 
CC1

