**CLINICAL STUDY FLOW CHART****Figure 1: Study Flow Chart**

## SCHE DULE OF EVENTS

Table 1: Schedule of Events

	Visit 1 Day 1 to Day 1	Visit 2 Day 1	Visit 3 Week 2 (± 3 Days)	Visit 4 Week 4 (± 3 Days)	Visit 4a 2 Weeks after touch-up (± 3 Days)	Visit 4b 4 Weeks after touch-up (± 3 Days)	Visits 5-9 Weeks 8-40 after baseline OR touch-up (± 5 Days)	Visit 10 or ET
Screening	Baseline / Tx	Follow-up	Follow-up / Touch-up	Follow-up	Follow-up	Follow-up	Follow-up	Follow-up
PROCEDURE								
Informed consent	X							
Medical history	X	X 						
Demographics	X							
Inclusion/exclusion	X	X 		X 				
Urine pregnancy test 	X	X 	X 	X 				
Treatment or touch-up		X		X 				
MLFS (investigator)	X	X 	X 	X 				
WAS upper perioral lines & oral commissures (investigator if applicable) 	X	X 		X 				
GAIS (subject and investigator)					X	X	X	X
Evaluate device deficiencies		X 		X 				
Photography		X 		X 				
Concomitant meds/procedures	X	X 	X	X 	X	X	X	X
Assessment of AEs	X	X 	X	X 	X	X	X	X

Abbreviations: GAIS, Global Aesthetic Improvement Scale; MLFS, Medicis Lip Fullness Scale; WAS, Wrinkle Assessment Scale

 Omit if the screening and baseline visits occur on Day 1 Prior to treatment Post treatment Omit if touch-up was not performed For females of childbearing potential Optional touch-up at Visit 4 to obtain optimal aesthetic improvement.  
*If a touch-up is performed, a 2wk and 4wk follow-up visits are scheduled (Visits 4a & 4b)* Subjects who are not treated in the upper perioral area or the right & left oral commissures at baseline (i.e. treated in the upper and lower lips only) are not required to have WAS assessed beyond

14(80)

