### 2.1.2 Effectiveness Objectives and Endpoints

The effectiveness objectives and endpoints are:

1. To evaluate the effectiveness of *Restylane Kysse* for lip augmentation as assessed by the investigator using the Medicis Lip Fullness Scale (MLFS) for the upper and lower lips.

Endpoints:

- a. Change from baseline at 8, 16, 24, 32, 40, and 48 weeks after last injection.
- b. Response rates (defined as at least 1-point improvement from baseline) at 8, 16, 24, 32, 40, and 48 weeks after last injection.

2. For subjects in the US: To evaluate the aesthetic improvement of the upper perioral rhytids and oral commissures after treatment with *Restylane Kysse* as assessed by the investigator using the Wrinkle Assessment Scale (WAS). *Note: After baseline, WAS will only be assessed for subjects who have been treated in the perioral area.*

Endpoints:

- a. Change from baseline at 8, 16, 24, 32, 40, and 48 weeks after last injection.

- b. Response rates (defined as at least 1-point improvement from baseline) at 8, 16, 24, 32, 40, and 48 weeks after last injection.
- 3. To evaluate the aesthetic improvement (overall appearance) of the upper and lower lips after treatment with *Restylane Kysse* as assessed by the subject and the investigator, independently, using the Global Aesthetic Improvement Scale (GAIS).

Endpoint:

- a. Response rates (defined as at least “Improved”) at 8, 16, 24, 32, 40, and 48 weeks after last injection.

CCI

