## 3. STUDY DESIGN

### 3.1 Overall Design

This is a prospective, open-label, multi-center study to evaluate the safety and effectiveness of *Restylane Kysse* for lip augmentation and correction of perioral rhytids, if applicable, in subjects with both biological parents of full Chinese descent.

Approximately 50 subjects with a score of 1 (Very Thin) or 2 (Thin) on the MLFS will be enrolled. The upper lip and lower lip scores do not have to be equal as long as each score is either 1 or 2 at baseline.

Following the informed consent and screening process, eligible subjects will be injected in the lips by the investigator at baseline. The method of injection is at the discretion of the investigator and will be recorded. Sufficient amount of product should be injected to achieve optimal aesthetic improvement as determined by the investigator and subject. Optimal aesthetic improvement is defined as at least 1-

point improvement from baseline using the MLFS and the best correction that can be achieved as agreed by the investigator and the subject.

Subjects in the US meeting the WAS inclusion criteria may also receive optional treatment with *Restylane Kysse* in the perioral rhytids at baseline. Treatment of the upper perioral lines, vermillion border, philtral columns, Cupid's bow, and/or oral commissures may be performed to obtain optimal aesthetic improvement, as agreed by the investigator and subject.

Touch-up treatment of the lips and perioral area, if treated at baseline, may be administered 4 weeks after baseline treatment if deemed necessary to obtain optimal aesthetic improvement; this decision should be agreed upon by the investigator and the subject. Touch-up treatment will not be performed if the subject has a disease or condition described in the exclusion criteria or is experiencing an ongoing treatment-related AE that, in the opinion of the investigator, would be worsened by touch-up treatment.

The recommended maximum injected volume per subject per treatment visit is 6 mL (i.e. 1.5 mL for the upper lip, 1.5 mL for the lower lip, and 3 mL for perioral area). Treatment will be performed according to the approved IFU.

Subjects will have in-clinic follow up visits at 2, 4, 8, 16, 24, 32, 40, and 48 weeks after the last injection. If a touch-up is deemed necessary and performed at 4 weeks post-baseline, a second 2-week and 4-week follow-up visits should be scheduled. See flowchart ([Figure 1](#)).

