### 6.2 Wrinkle Assessment Scale

The WAS is a validated photograph-based outcome instrument that is designed specifically for quantifying facial folds. Scoring of fold severity is based on visual assessment of the length and apparent depth of the wrinkle at a certain time-point. Scoring of the upper perioral rhytids and oral commissures according to Table 5 will be based on visual live assessment by the investigator at defined time points, and not on a comparison to the baseline appearance. Change from baseline (Day 1, pre-treatment) in the WAS will be calculated for each post baseline assessment.

After the baseline visit, WAS will only be assessed for subjects who have been treated in the perioral area.

The WAS photo guides for the upper perioral rhytids and oral commissure are provided in [Appendix 2](#).

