#### 2.4.3.2 Wrinkle Assessment Scale

WAS will be presented with number of subjects and percentage for each category of the scale. The proportion of responders based on the WAS (i.e., at least a one point improvement from the investigator baseline assessment of the upper perioral rhytids and oral commissures at weeks 8, 16, 24, 32, 40, and 48) will be calculated and presented along with their 95% confidence intervals (calculated via Clopper-Pearson). A bar plot of the percentage of responders for each upper perioral rhytids and oral commissures by visit also will be produced for each.

In addition, the change from baseline at weeks 8, 16, 24 32, 40, and 48 after last injection will be calculated. The number of subjects and percentage for each point change (+3, +2, +1, 0, etc.) from baseline will be presented.

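### On the readable text, WAS response is plotted per area while rating after baseline is set per subject, so a subject can count in the rate for an area that was not injected

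*Protocol*

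**What the plan says.** **Display.** For the WAS, SAP 2.4.3.2 states: "A bar plot of the percentage of responders for each upper perioral rhytids and oral commissures by visit also will be produced for each". The same section and Protocol 9.5.2 give a response proportion with a 95% interval, but do not say whether the tabulated proportion is per area or combined. Only the plot is explicitly per area.

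**Denominator.** Protocol 9.4 gives the responder formula as follows: "regarding WAS will be calculated as (number of subjects (or upper/lower lips) with at least one grade improvement from baseline/number of subjects reporting", counted visit by visit. All effectiveness variables use the MITT population, which is defined by treatment of both lips (Protocol 9.2, SAP 2.2.1), on observed cases (SAP 2.4.2). SAP 2.8 reports no substantial change from the protocol's methods.

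**Injection.** Protocol 3.1 lists the optional perioral sites and ends the list with "and/or oral commissures may be performed to obtain optimal aesthetic improvement". SAP 1.1.1 has the same list, so one rated area may be injected without the other.

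**Rating after baseline.** The wordings differ:
- Protocol Synopsis: "WAS will only be assessed for subjects who have been treated in the upper perioral rhytids or the oral commissures".
- Protocol 2.1.2, repeated in SAP 1.2.1: "After baseline, WAS will only be assessed for subjects who have been treated in the perioral area".
- Protocol 6.2, repeated in SAP 1.3.2: "After the baseline visit, WAS will only be assessed for subjects who have been treated in the perioral area".
- Protocol Table 1 has one row for both areas, "WAS upper perioral lines & oral commissures (investigator if applicable"). Its footnote 7 begins "Subjects who are not treated in the upper perioral area or the right & left oral commissures at baseline", explains that this means subjects treated in the lips alone, and exempts them from later WAS rating. The end of the footnote is cut off in the readable copy.

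**The concern.** Objective 2 concerns improvement of the rhytids and commissures after treatment. A reader will take the bar for an area as the response where that area was treated. If the bar also includes subjects who were rated there but injected elsewhere, it mixes treated and untreated skin, and the plot gives no sign of it. If uninjected areas improve less often, the bar understates the effect of injection. How many such subjects contribute may also differ between the two areas, so comparing the two bars could mislead.

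**Working it through.** **1. Is there a plan figure to reproduce?** No. Protocol 9.12 and SAP 2.7 say that the sample of about 50 was not calculated. The documents give no expected WAS rate, no number of subjects with perioral treatment, and no share injected in one area only.

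**2. Who is rated, and where can they count?** This table applies the readable rules to each injection pattern.

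| Perioral sites injected | Rated under Synopsis wording | Rated under perioral-area wording | Rates the subject can enter without injection there |
|---|---|---|---|
| Rhytids and commissures | Yes | Yes | None |
| Commissures only | Yes | Yes | Rhytids |
| Rhytids only | Yes | Yes | Commissures |
| Only vermillion border, philtral columns or Cupid's bow | No | Yes | Both, under the wider wording |

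Reading the denominator as subjects with a score for that area does not change the table, because no readable text limits scoring to injected areas.

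**3. Effect on the rate.** Let u be the share of rated subjects not injected in the area, r1 the response where injected and r0 the response where not.

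- All-rated rate = (1 − u) × r1 + u × r0
- Fall relative to the injected rate = u × (r1 − r0)
- Because r0 cannot be negative, the all-rated rate is at least (1 − u) × r1.

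Assumed ranges, none from the documents: r1 from 60% to 90%, r0 from 0% to 20%. The gap r1 − r0 then runs from 60 − 20 = 40 points to 90 − 0 = 90 points.

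| u | Smallest fall | Largest fall |
|---|---|---|
| 0% | 0 | 0 |
| 10% | 0.10 × 40 = 4 points | 0.10 × 90 = 9 points |
| 25% | 0.25 × 40 = 10 points | 0.25 × 90 = 22.5 points |
| 50% | 0.50 × 40 = 20 points | 0.50 × 90 = 45 points |

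**4. Illustration with the SAP's interval method** (two-sided 95% Clopper-Pearson). Assumed counts: a quarter of rated subjects not injected in the area, none of them responding.

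| Rated | All-rated rate | Injected-area rate |
|---|---|---|
| 20 | 12/20 = 60% (36.1 to 80.9) | 12/15 = 80% (51.9 to 95.7) |
| 40 | 24/40 = 60% (43.3 to 75.1) | 24/30 = 80% (61.4 to 92.3) |

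In this example the estimate shifts by 20 points and the intervals overlap.

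**The case against.** The strongest reply is that the rule may sit in text that cannot be read. SAP 2.1.3 Data Transformations, the counterpart of Protocol 9.4, is redacted. So are the WAS inclusion criteria. Footnote 7 is cut off, and SAP 2.1.2 puts table and figure formats in a companion document. SAP 2.1 also says that the SAP supersedes the protocol's statistical sections, and 2.8 denies only substantial changes. This stands: a reader might infer that the plan has no per-area denominator, but the documents do not support that. What can be said is that none is visible.

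A second reply is that the Table 1 row is qualified as applying only where applicable, which could mean that only injected areas are scored. The denominator would then already be area-specific. Footnote 7 points the other way: it describes the exempt subjects as those treated in the lips alone, which makes the exemption a per-subject one.

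A third reply is that the all-rated rate matches the population note to Objective 2 and the MITT rule. That is correct, and the all-rated rate is a valid row to keep. It does not answer a different question: the response where the area was treated.

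A fourth reply is that little turns on it. There is no WAS test or threshold, any dilution by less responsive uninjected areas is conservative, and SAP 2.5.1 summarizes injection by location. This supports a low rating. It does not let a reader of the plot see the mixture.

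**Conclusion.** The point holds as a minor one, on the readable text. Following the stated rules, a subject can count in the WAS rate of an area that was not injected. The size is unknown. It is zero if every rated subject was injected in both areas. Otherwise it is the uninjected share times the gap in response, and every value used above for these is an assumption. In particular, nothing in the documents suggests that as many as half of rated subjects would be uninjected in an area.

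A reader might infer that the planned WAS results are biased or the all-rated rate wrong. The documents support neither. Whether any rated subject lacked injection in one area is not known, only the plot is explicitly per area, and the endpoint is descriptive, optional and limited to US subjects. Nor do the documents show that Week 4 opens the perioral area to new subjects: Protocol 3.1, 3.4.4 and 5.5.3 limit perioral touch-up to those treated there at baseline. First injection of a particular site at Week 4 in such a subject is not excluded, but it is not shown either.

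**What to change.** In SAP 2.4.3.2, for each WAS area:
1. Report the response rate and Clopper-Pearson interval among MITT subjects who were injected in that area before the assessment and have both a baseline score and a score at that visit.
2. Keep the all-rated rate as a second row, and label which row the bar plot shows.
3. If SAP 2.1.3 or the companion formats already set the per-area denominator, a cross-reference in 2.4.3.2 will serve for the denominator.

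Reconcile the Protocol Synopsis, Protocol 2.1.2 and 6.2, Table 1 footnote 7, and SAP 1.2.1 and 1.3.2 on who is rated after baseline. The reference to lips in the Protocol 9.4 WAS formula is a wording slip and can be corrected at the same time.

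**Cost.** SAP wording, one extra row per area, and one flag for area treated. Protocol 5.5.9 records needle or cannula by treatment area and SAP 2.5.1 summarizes by location, but neither shows that rhytids and commissures are captured separately. If they are not, the flag must come from source treatment records. Denominators shrink, so intervals widen at the same rate: at 80%, 16/20 gives an interval 37.9 points wide (56.3 to 94.3 after rounding) and 12/15 one 43.8 points wide.
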